# **Observation period of safety endpoints**

The observation period of safety data will be divided into 3 segments:

- The **pre-treatment period** is defined as the time between the date of the informed consent and the first injection of open-label IMP
- The **on-treatment period** is defined as the time from the first injection of open-label IMP up to 7 days after the last injection of open-label IMP, regardless of the introduction of rescue therapy. The 7-day interval is chosen based on the half-life of the IMP (approximately 5 times the half-life of Tresiba)
- The **post-treatment period** is defined as the time starting 8 days after the last injection of open-label IMP (after on-treatment period)

The baseline value for safety endpoints will be the last available value prior to the first injection of open-label IMP.

# 9.2.2.1 Adverse events

Refer to Section 10.4 to Section 10.7 for details.

# 9.2.2.2 Hypoglycemia

Hypoglycemia will be assessed. Refer to Section 10.6.1 for details.

# 9.2.2.3 Body weight

Body weight should be obtained with the patient wearing undergarments or very light clothing and no shoes, and with an empty bladder. The same scale should be used throughout the study, and calibrated on a regular basis as recommended by the manufacturer.

The use of balance scales is recommended; if digital scales are used, testing with standard weights is of particular importance. The floor surface on which the scale rests must be hard and should not be carpeted or covered with other soft material. The scale should be balanced with both weights at zero and the balance bar aligned. The patient should stand in the center of the platform as standing off-center may affect measurement. The weights are moved until the beam balances (the arrows are aligned). The weight is read and recorded in the e-CRF and Source Data. Self-reported weights are not acceptable; patients must not read the scales themselves. The body weight is measured at each on-site visit.

# 9.2.2.4 Laboratory safety variables

The clinical laboratory data consist of blood analysis, including hematology, clinical chemistry, serum pregnancy test in females of childbearing potential and serum follicle stimulating hormone (FSH) and estradiol (only in females requiring confirmation of postmenopausal status) and urinalysis. Clinical laboratory values will be analyzed after conversion into standard international units. International units will be used in all listings and tables.

Central laboratory data will be collected only at screening visit (Visit 1, Week -2) for identifying patients with exclusion criteria or safety consideration include serum pregnancy test will be test at screening visit. Urine pregnancy test at site will be performed at Visit 2 and end of treatment visit.

# 9.2.2.5 Physical examination

Physical examination is performed at screening visit (V1, Week-2), baseline visit (V2, Day 1) and end of treatment visit (V20, Week 24). Height is measured at V1 (see Section 1.2).

# 9.2.2.6 Vital signs

Vital signs include: systolic and diastolic blood pressure (mmHg) and heart rate (beat per minute: bpm). They are assessed at screening (Visit 1, Week -2); at baseline (Visit 2, Day 1), and all on-site visit (see Section 1.2).

Blood pressure (mmHg) should be measured when the patient is quiet and seated and with their arm outstretched in line with mid-sternum and supported. Measurement should be taken under standardized conditions, approximately at the same time of the day, on the same arm, with the same device (after the patient has rested comfortably for at least five minutes) and the values are

to be recorded in the e-CRF. Both systolic blood pressure (SBP) and diastolic blood pressure (DBP) should be recorded. Devices for blood pressure measurement should be regularly recalibrated according to manufacturers' instructions.

Heart rate (bpm) will be measured at the time of the measurement of blood pressure.

#### Determination of the arm for blood pressure measurements:

At Visit 1 of the screening period, blood pressure has to be measured on both of the arms after 5 minutes in seated position and then again after two minutes in both arms in seated position. The arm with the higher diastolic pressure will be determined at this visit, identifying the reference arm for future measurements throughout the study. The highest value will be recorded in the e- CRF (all blood pressure values are to be recorded in the source data).

# 9.3 OTHER ENDPOINTS

# 9.3.1 Patient Reported Outcomes (Health-related Quality of Life)

The patient reported outcomes (PROs) measures in this study are the Treatment Satisfaction Questionnaire (DTSQs and DTSQc versions) and the Hypoglycemia Attitudes and Behavior Scale (HABS). They will be administered at Week 0 (Day 1, except for DTSQc), at Week 12 and at the end of the treatment. The questionnaires are attached in the Appendices (see Appendix A, Appendix B, Appendix C)

The patients will be requested to complete the questionnaires by themselves during selected clinical visits (see study flow chart) in specific booklets, independently from investigator, site staff and any help from friends or relatives. For validity purposes, patients will be asked to answer all the questions of the questionnaires at the start of the visit in a quiet place, and while on site to return the completed questionnaires to the investigator or his/her designee on the same day.

In case of rescue therapy: Administration of the three questionnaires (DTSQs, DTSQc and HABS) prior to the administration of the rescue therapy and afterwards as normally planned.

In case of early IMP discontinuation: Administration of the questionnaires at the visit planned for the last dosing day with IMP and afterwards as normally planned.

**The Diabetes Treatment Satisfaction Questionnaire Status Version (DTSQs)** is a validated questionnaire to assess patient satisfaction with treatment and patient perception of blood glucose control (11). It consists of 8 items that are answered on a Likert scale from 0 to 6. Items 1, 4, 5, 6, 7 and 8 are summed to produce a Total Treatment Satisfaction score ranging from 0 (no satisfaction) to 36 (high satisfaction with treatment). The 2 items of 'perceived frequency of hyperglycemia' (Item 2) and 'perceived frequency of hypoglycemia' (Item 3) are scored separately ranging from 0 (none of the time) to 6 (most of the time). DTSQs will be administered at baseline, 12 and 24 weeks in the local language.

**The Diabetes Treatment Satisfaction Questionnaire Change Version (DTSQc)** was developed from the original DTSQ to evaluate the change in treatment satisfaction at a specific time point (12). The change version has the same 8 items as the status version, with a small alteration to the wording of Item 7. The DTSQc instructions and response options differ from those of the DTSQs to produce measures of relative change in satisfaction rather than measures of absolute satisfaction. Items are answered on a Likert scale from -3 to +3, and the sum of the treatment satisfaction scores range from -18 to +18. Positive scores are indicative of improvement in treatment satisfaction, whereas negative scores are indicative of deterioration in treatment satisfaction. A score of 0 represents no change. The 2 items of 'perceived frequency of hyperglycemia' (Item 2) and 'perceived frequency of hypoqlycemia' (Item 3) are scored from -3('much less of the time now') to +3 ('much more of the time now'), meaning negative scores indicate fewer problems with blood glucose levels and positive scores indicate more problems than before. DTSQc will be administered at 12 and 24 weeks in the local language.

At 12 and 24 weeks, DTSQs (status) will be administered before the DTSQc (change).

The **HABS (Hypoglycemia Attitudes and Behavior Scale)** was recently developed with type 2 diabetic patients using or not insulin (13). It consists of 14 items within 3 domains measuring anxiety (5 items), confidence (5 items) and avoidance (4 items) related to hypoglycemia. Items are answered on a Likert scale from 1 (strongly disagree) to 5 (strongly agree), with higher scores indicating high avoidance, confidence and anxiety related to hypoglycemia. The questionnaire will be administered at baseline, 12 and 24 weeks in the local language.

# 9.4 FUTURE USE OF SAMPLES

Not applicable

# 9.5 APPROPRIATENESS OF MEASUREMENTS

The primary efficacy endpoint of this study is change of HbA1c from baseline to endpoint (scheduled Week 24). HbA1c reflects the average glycemia over 2-3 months and has strong predictive value for diabetes complications. It is accepted by regulatory agencies and scientific association as an appropriate primary endpoint to support a claim based on glycemic control. Twenty-four weeks duration of study treatment is considered to be sufficient for achieving steady state conditions with Toujeo or Tresiba enabling an adequate assessment of time-dependent changes in HbA1c and the concomitant risk of hypoglycemia.

Most international consensus statements for standards of medical care in diabetes recommend to decrease HbA1c <7% to minimize the risk of developing complications. An even tighter threshold of HbA1c  $\leq 6.5\%$  is recommended in some guidelines (15). T2DM patients with HbA1c values in the target range and experiencing no hypoglycemia episodes are considered optimally managed for the disease. Secondary objectives are to analyze responder which is intended to justify clinical relevance of the observed reduction in HbA1c values. Therefore, analysis of responders is set up to compare both formulations in terms of rate of patients achieving and/or maintaining optimal long-term glycemia control confirmed by target HbA1c <7% or  $\leq 6.5\%$  and without experiencing confirmed hypoglycemia (70 mg/dL and 54 mg/dL as cut-off point).

Property of the Sanofi Group - strictly confidential

Change in FPG is an acceptable secondary efficacy endpoint by regulatory agencies (15),(16) and scientific association. Change in 24-hour average plasma glucose, assessed as mean of 8 measurements in each 8-point SMPG profile, is an acceptable secondary efficacy endpoint by regulatory agencies. Lower diurnal fluctuation of glycemia in insulin-treated T2DM patients accounts for decrease in the frequency of episodes of hypoglycemia or hyperglycemia. The secondary endpoint of variability of plasma glucose is set up to assess if longer duration of action of the new formulation of insulin and less fluctuation in systemic exposure favorably affect variability of plasma glucose. The analysis will be based on self-monitored plasma glucose measurements (eg, 4-point and 8-point glucose profiles, fasting plasma glucose).

Safety evaluation will be evaluated by standard clinical and laboratory measurement, including the comparison of all hypoglycemia events occurrence frequency and distribution. Nocturnal hypoglycemia timeframe is defined as during standardized period (0:00 to 5:59 AM) and extended period (0:00 to 7:59 AM) and at sleep status to observe the hypoglycemia event when patients are usually at sleeping period, usually in fasting condition. Specific safety parameters of interest for a glucose lowering injectable peptide such as injection site reactions and hypersensitivity will also be assessed. Other TEAE will be evaluated and summarized.

Repeat assessment of PROs will be performed throughout the study (Including diabetes treatment satisfaction, perception of hypoglycemia and hyperglycemia questionnaires [DTSQs and DTSQc] and Hypoglycemia Attitudes and Behavior Scale [HABS].

# 10 STUDY PROCEDURES

# 10.1 VISIT SCHEDULE

The visit schedule and procedures/assessments listed in the "Study Flow Chart" in Section 1.2 are not repeated in this section. The aim of this section is to provide details on how some of the procedures/assessments have to be performed.

This is an outpatient study and consists of 9 on-site visits and 12 phone-call visits. Additional, optional phone call visits to monitor insulin titration should be scheduled whenever considered necessary by the investigator. All on-site visits should take place in the morning at approximately the same time (patient is in **fasting conditions** at Visit 1 (Week -2, screening visit), Visit 2 (Day 1, baseline), Visit 10 (Week 8), Visit 14 (Week 12), Visit 20 (Week 24), see also Study Flowchart, Section 1.2).

The **fasting condition** is defined as an overnight fast no less than 8 hours that consisted of no food or liquid intake, other than water. IMP and non-insulin antidiabetic medication should be administered after the fasting blood sample is drawn for all laboratory tests on the study site.

**Note:** If the patient is not in fasting conditions at visits which required in fasting conditions, the blood sample is not collected and a new appointment should be given to the patient for the following day if possible, with instruction to be fasted.

For phone-call visits, the patient is called by the investigator or qualified designee at a scheduled time.

Visit window: From Visit 3 (Week 1) to Visit 9 (Week 7), a timeframe of  $\pm$  3 days is acceptable using the day of visit 2 (baseline) as reference (if one visit date is changed, the next visit should take place according to the original schedule). From Visit 10 (Week 8) up to the final primary endpoint assessment at Visit 20 (Week 24), a time frame of  $\pm$  5 days is acceptable. For Visit 21 (follow up visit) a time frame of -1~+3 day post-treatment is acceptable.

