Both Toujeo and Tresiba took Lantus as active comparator and demonstrated comparable efficacy and lower hypoglycemia risk in T2DM but no head-to-head comparison was performed. This trial is designed to confirm Toujeo's efficacy and safety in comparison with Tresiba in insulin-naïve patients with T2DM inadequately controlled with non-insulin anti-diabetic medication and requiring basal insulin initiation. It will test the hypothesis that glucose control with Toujeo is non-inferior to Tresiba. Based on the currently available medical evidence and the application of the treat-to-target concept, comparable efficacy is expected. HbA1c reflects the average glycemia over 2-3 months and has strong predictive value for diabetes complications. It is accepted by regulatory agencies, scientific association as an appropriate primary endpoint to support a claim based on glycemic control (9),(10).

In the EDITION trials Toujeo was associated with lower hypoglycemia risk than Lantus during the initial phase (first two months when most of the insulin titration occurred) and the hypoglycemia benefit was maintained until the end of the trials (6 months) in T2DM. Tresiba demonstrated comparable hypoglycemia risk to Lantus during the titration phases (0-15 weeks of treatment) and in favor of Tresiba with lower hypoglycemia risk beyond Week 16 in insulin naive population (6). Hence, the results from this head to head comparison of Toujeo with Tresiba in term of hypoglycemia will be of particular interest.

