# 9 ASSESSMENT OF INVESTIGATIONAL MEDICINAL PRODUCT

In case of using rescue therapy, all assessments planned for the Visit 20 (Week 24) are to be performed before initiating rescue therapy. After these assessments are completed and rescue therapy has been initiated, the patient will remain in the study and continue with their study treatment as well as background non-insulin anti-diabetic drugs if appropriate. The planned visits and assessments should be performed until the last scheduled visit.

In case of premature and permanent IMP discontinuation, patients should have a visit as soon as possible with the assessments normally planned in Visit 20 (Week 24). Afterward, the patients should continue in the study up to the scheduled date of study completion. They should be followed up according to the study procedures as specified in the protocol (except for the 7-day safety post-treatment follow-up).

Data quality being very important to fully evaluate the efficacy/safety of the IMP, investigators must make their best efforts educating their patients on the importance of sticking to visit schedules, study required procedures and assessments up to the end of the study. A particular effort is requested to prevent missing data.

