The following secondary endpoints will be analyzed using logistic regression model adjusted on randomization strata of screening HbA1c (<8.0%, $\geq8.0\%$) and randomization strata of SU or meglitinides at screening (yes/no). This model will also estimate the Odds Ratio of Toujeo and Tresiba and its corresponding 95% CI.

- Percentage (%) of patients reaching target HbA1c <7% and ≤6.5% at Week 12 and Week 24,
- Percentage (%) of patients reaching target HbA1c <7% at Week 24 without severe and/or confirmed hypoglycemia (≤70 mg/dL) during the 24 weeks treatment period,
- Percentage (%) of patients reaching target HbA1c <7% at Week 24 without severe and/or confirmed hypoglycemia (<54 mg/dL) during the 24 weeks treatment period,
- Percentage (%) of patients reaching target HbA1c <7% at Week 12 without severe and/or confirmed hypoglycemia (≤70 mg/dL) during the 12 weeks treatment period,
- Percentage (%) of patients reaching target HbA1c <7% at Week 12 without severe and/or confirmed hypoglycemia (<54 mg/dL) during the 12 weeks treatment period,
- Percentage (%) of patients reaching target HbA1c ≤6.5% at Week 24 without severe and/or confirmed hypoglycemia (≤70 mg/dL) during the 24 weeks treatment period,
- Percentage (%) of patients reaching target HbA1c ≤6.5% at Week 24 without severe and/or confirmed hypoglycemia (<54 mg/dL) during the 24 weeks treatment period,
- Percentage (%) of patients reaching target HbA1c ≤6.5% at Week 12 without severe and/or confirmed hypoglycemia (≤70 mg/dL) during the 12 weeks treatment period,
- Percentage (%) of patients reaching target HbA1c ≤6.5% at Week 12 without severe and/or confirmed hypoglycemia (<54 mg/dL) during the 12 weeks treatment period,
- Percentage (%) of patients with SU or meglitinide dose reduction due to hypoglycemia,

• Percentage of patients requiring rescue therapy during 24 weeks treatment period.

Hypoglycemia will be determined during the 12-week on-treatment period and the 24-week on treatment period, respectively (used for efficacy endpoint, as defined in Section 2.1.3).

Patients who initiate rescue therapy during the 12-week on-treatment period or during the 24-week on treatment period, respectively, will be considered as failure for this given period.

Patients with missing HbA1c at a given visit will be considered as failure (non-responders) for this given visit.

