2.5.2 Data handling conventions for secondary efficacy variables

Fasting condition

FPG measurement not collecting in fasting condition will not be used in the analyses.

Invalid laboratory data

HbA1c or FPG measurements flagged as invalid by the laboratory will not be used in the analyses.

HbA1c target

HbA1c target missing data handling

• Patients with missing HbA1c data at respectively Week 12 and Week 24 will be regarded as not having reached the HbA1c target (ie, as failure) at each given time-point.

Composite endpoints missing data handling

- For each cases presented above regarding missing HbA1c values the patient will be considered as failure for each composite endpoint of the corresponding randomized period,
- For each case presented above regarding missing hypoglycemia event information the patient will be regarded as failure for each related composite endpoint,
- In case of premature end of study during the 24 weeks randomized period the patient will be considered as failure for each composite endpoint relative to the 24 weeks period.

Change in HbA1c category

Patients with missing:

- Baseline HbA1c will be regarded as not having reached the HbA1c target at Week 12 and Week 24,
- HbA1c data at respectively at Week 12 and Week 24 will be regarded as not having reached the HbA1c target at each given time-point.

HABS

The Hypoglycemic Attitudes and Behavior Scale consists of 14 items within 3 domains measuring anxiety (5 items), confidence (5 items) and avoidance (4 items) related to hypoglycemia. The 3 domain scores are determined by computing the mean of item responses. At least 2/3 of the items should be completed for the calculation of each domain score, which means only one item missing is acceptable to calculate each domain score. If more than one item is missing, the domain score is considered as missing.

DTSQc and DTSQs

The total treatment satisfaction score is the sum of items 1, 4, 5, 6, 7 and 8.

If no more than 2 out of the 6 questions comprising the total treatment satisfaction score are missing, the total treatment satisfaction score is imputed by calculating the average of the scores from the answered questions, dividing this sum by the number of answered questions and multiplying the average by six.

If items 2 or 3 are not answered, frequency of hypoglycemia or hyperglycemia scores is considered as missing.

• In- between scores

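### Section 10.1 withholds the HbA1c sample along with FPG when a patient arrives non-fasting: a small, avoidable risk of missing primary-endpoint data

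*Protocol*

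**What the plan says.** Protocol section 10.1 names V1, V2, V10, V14 and V20 as fasting visits. It treats the draw at these visits as one sample: "IMP and non-insulin antidiabetic medication should be administered after the fasting blood sample is drawn for all laboratory tests on the study site". The note that follows covers a patient who arrives non-fasting: "the blood sample is not collected and a new appointment should be given to the patient for the following day if possible".

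The flow chart and section 9.1.1 place HbA1c at the same five visits, with V20 as the primary-endpoint assessment. FPG is drawn at V2, V10, V14 and V20 (section 9.2.1.1). Hematology and clinical chemistry are scheduled at V1 only, and pregnancy tests after V1 use urine. At V10, V14 and V20 the scheduled central-laboratory blood tests are therefore HbA1c and FPG and nothing else.

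On whether fasting matters, protocol section 4 says that "HbA1c reflects the average glycemia over 2-3 months". The fasting rule in SAP section 2.5.2 concerns FPG alone: "FPG measurement not collecting in fasting condition will not be used in the analyses". HbA1c is dropped there only if the laboratory flags it as invalid. On missing data, protocol section 9 says: "A particular effort is requested to prevent missing data".

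**The concern.** The only two blood tests at V20 are HbA1c and FPG, so an instruction not to take the sample withholds both. Only FPG needs the fast. The protocol thus tells sites to forgo, at least for that day, a primary-endpoint value that its own SAP would accept. This also runs against the request in section 9 to prevent missing data.

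If the Week 24 HbA1c is never obtained, the plan sets three consequences:

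- The primary MMRM handles it as missing at random (SAP 2.4.4.1.1).
- The patient leaves the per-protocol population, which requires an on-treatment Week 24 HbA1c (SAP 2.3.1.2).
- The patient is a non-responder on the HbA1c-target endpoints and their hypoglycemia composites, whatever the true value: "Patients with missing HbA1c at a given visit will be considered as failure (non-responders) for this given visit" (SAP 2.4.4.2.1).

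**Working it through.** **Does the rule reach HbA1c?** Yes, as written. The fasting visits and the HbA1c visits are the same five, the sample is described as serving all laboratory tests, and neither document exempts HbA1c.

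**When is the value actually lost?** The safeguards are:

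- a new appointment, on the following day where possible (protocol 10.1);
- a visit window of ±5 days from V10 to V20 (protocol 10.1);
- an on-treatment period for HbA1c that runs to 7 days after the last dose or to the start of rescue, whichever is earlier (SAP 2.1.3);
- no re-allocation of nominal visits, so a late sample recorded as V20 remains Week 24 (SAP 2.5.4);
- use of unscheduled central-laboratory values for endpoint values (SAP 2.5.5). This is a weaker backstop, because SAP 2.5.4 does not re-allocate unscheduled assessments and does not say how one becomes a Week 24 value.

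Two routes to loss remain:

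1. *V20.* The patient does not return within about a week. No scheduled HbA1c follows V20.
2. *Premature discontinuation.* The return falls more than 7 days after the last dose. The value then leaves the on-treatment analysis but still enters the randomized-period sensitivity analysis (SAP 2.4.4.1.3). Because SAP 2.5.4 assigns the end-of-treatment value to the next due on-site visit, the value lost may belong to an earlier visit than Week 24. These patients are outside the per-protocol population in any case.

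**Size in terms of power.** The inputs, from protocol 11.1 and SAP 1.3, are margin 0.3, SD 1.4, true difference 0, one-sided α 0.025, power 90% and 460 per arm.

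The plan's own figure: n per arm = 2 × 1.4² × (1.960 + 1.282)² / 0.3² = 458 after rounding up, or 916 in total. The noncentral-t calculation first reaches 90% at 459 per arm. The stated 460 per arm (920) is reproduced, with a surplus of only 1 to 2 patients per arm.

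Power = Φ(0.3 / (1.4 × √(2/n)) − 1.960). At n = 460 this is Φ(3.250 − 1.960) = 90.1%.

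The documents give no loss rate, so the rates below are assumptions. Lost patients are taken to contribute nothing, which is the worst case for power:

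| Assumed loss of Week 24 values | Effective n per arm | Power |
|---|---|---|
| 0% | 460.0 | 90.1% |
| 1% | 455.4 | 89.9% |
| 3% | 446.2 | 89.3% |
| 5% | 437.0 | 88.6% |

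The MMRM recovers part of this from the Week 8 and Week 12 values.

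**The case against.** The strongest reply is that the rule delays the sample and seldom loses it. That is largely right, and it rules out several stronger readings.

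- *A reader might infer that a patient who cannot come back the next day loses the Week 24 value.* The words on possibility most naturally qualify the following day, not the appointment itself, and the windows above leave about a week.
- *A reader might infer that the delay pushes the pre-rescue sample outside its window.* Protocol sections 8.3.2 and 9 require the V20 assessments before rescue starts. If that is followed, the rebooked sample still falls inside the on-treatment period.
- *A reader might infer that baseline HbA1c is also at risk.* Randomization follows completed baseline assessments (protocol 8.5 and 10.1.2.1). Baseline is the last value before the first injection, so the screening HbA1c is a fallback.
- *A reader might infer bias from losses concentrated in less adherent patients.* The documents offer no evidence for this. The rule is the same in both arms, and the penalized imputation and tipping-point analyses already examine departures from missing at random (SAP 2.4.4.1.4).

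Two further points carry weight. Protocol section 9.1 leaves sampling detail to a separate manual, not available here, which may already separate the two samples. In addition, the per-protocol analysis is a sensitivity analysis, and p-values for the secondary endpoints are descriptive (SAP 2.4.4.4).

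What stands is that the text in 10.1 contains no exception for HbA1c and that withholding the sample gains nothing for the analysis. If the manual does allow the draw, it conflicts with 10.1 and the two should be aligned.

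**Conclusion.** The concern holds as a small, avoidable risk of missing HbA1c, not as a systematic loss of the primary endpoint. It rests on reading the blood sample in 10.1 as including HbA1c, which the visit schedule supports. It also rests on HbA1c not needing a fast. The documents do not say this outright, but it follows from their description of HbA1c as a 2-3 month average and from the FPG-only exclusion in the SAP.

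The number of patients affected cannot be derived from the documents. Someone might assume that 2-5% arrive non-fasting at V20 and that 20-50% of those are never sampled in time. That would give 0.02 × 0.20 × 920 ≈ 4 to 0.05 × 0.50 × 920 = 23 patients, but both rates are guesses. At losses of this order the cost in power is under one percentage point. The reason to act is that the loss is easy to prevent, not that it threatens the trial's conclusion.

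**What to change.** Amend the note in protocol section 10.1, and align the laboratory manual, to say the following: if the patient is not fasting at V10, V14, V20, the end-of-treatment visit or the pre-rescue visit, the HbA1c sample is collected at that visit, and only the FPG sample is deferred to a fasting re-visit, which should still be booked.

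The change takes one sentence in each document and needs no change to the SAP, which already discards non-fasting FPG and accepts HbA1c regardless of fasting. The cost is a second draw for the few patients who return. With HbA1c already taken, site and patient may also have slightly less reason to complete the fasting re-visit, so a few more FPG values could be lost. FPG is a secondary endpoint and HbA1c the primary one, so the exchange is worth making.
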